**Figure 2-1 Study design Cohort 1 and Cohort 2**

[figure not shown]
Cohort 3, comprises two periods, namely:

1. open-label treatment period (from dosing on Day 1, Week 1 to last dose and completion of assessments on Day 85, Week 13),
2. follow-up period (from Week 13 to Day 141/Week 21), when patients will be followed up for 8 weeks without study medication.

In the open label period, treatment arm 1 dosing starts with CFZ533 s.c. q1w for 4 weeks, whereas in treatment arm 2, dosing starts with CFZ533 i.v. on Day 1. In both arms maintenance dosing then continues with CFZ533 s.c. q1w for 4 weeks (treatment arm 1) or 9 weeks (treatment arm 2).

An illustration of the study design for Cohort 3 is provided in Figure 2-2.

**Figure 2-2 Study design Cohort 3**

### **3 First interpretable results (FIR)**

First interpretable results (FIR) will be provided for this trial but not as fully as usual due to interim analyses that have already occurred. Corporate Confidential Information

Corporate Confidential Information

The template shows the analysis / results to be presented in the FIR. Study outputs required to be created at the time of the FIR will be marked as “Key” in the Tracking sheet output list.

Corporate Confidential Information

## 5 Statistical methods: Analysis sets

For subjects for which the actual treatment received does not match the randomized treatment the treatment actually received will be used for the analysis.

All subjects that received study drug and with no protocol deviations with relevant impact on safety will be included in the safety analysis set.

The PK analysis set will include all subjects with available PK data and no protocol deviations with relevant impact on PK data.

The PD analysis set will include all subjects with available PD data and no protocol deviations with relevant impact on PD data.

The analysis sets and protocol deviation codes are related as follows:

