9.1 Analysis sets

For all analysis sets, subjects will be analyzed according to the study treatment received.

The full analysis set will include all subjects that received any study drug.

The safety analysis set will include all subjects that received any study drug.

The PK analysis set will include all subjects with available PK data and no protocol deviations with relevant impact on PK data.

The PD analysis set will include all subjects with available PD data and no protocol deviations with relevant impact on PD data.

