**Table 5-1 Protocol deviation severity codes and analysis sets**

Protocol deviation severity code		Safety analysis set	PK analysis set	PD analysis set
Code	Text			
5	Exclude subject from all safety analysis	-	-	-
8	Exclude from all analyses	-	-	-
20	Exclude subject from PK analysis set	+	-	+
22	Exclude subject from PD analysis set	+	+	-
23	Exclude subject from PK and PD analysis set	+	-	-
49	Report relevant protocol deviation – include subject in all analysis sets	+	+	+

+ = include in analysis set, - = exclude from analysis set, NA = not applicable

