## **7 Statistical methods for Pharmacodynamic (PD) parameters**

### **7.1 Analysis of the primary variable**

#### **7.1.1 Statistical model, hypothesis, and method of analysis**

The primary efficacy variable is the ESSDAI change from baseline.

It is assumed that the ESSDAI will follow an approximate normal distribution. If this assumption appears to not be met, alternative statistical methods may be applied. For example, data may be log transformed with changes from baseline in the log transformed data being analyzed.

The analysis of the data for the primary variable from Cohorts 1 and 2 differs from that proposed in the protocol in that it will not be conducted combining placebo data from those two cohorts. Being in two separate consecutive cohorts, one s.c. and the other i.v., they are not now considered similar enough to combine. As a result, the active treatments under consideration, Corporate Confidential Information are each compared to their respective matching placebo treatments within each cohort. Cohort 3 simply compares two alternative loading regimes.

For each of cohorts 1 and 2, a longitudinal model describing ESSDAI change from baseline over time will be fitted up to Week 13 with the following fixed effect terms: baseline ESSDAI, treatment group, visit, and interaction between treatment group and visit. In the first instance an unstructured variance-covariance matrix will be fitted; if there are issues with convergence then other variance-covariance matrices will be investigated. The change from baseline in ESSDAI at Week 13 (end of placebo-controlled period) will be estimated from the model. Inference will be done in the frequentist framework.

For Cohorts 1 and 2 the results from the primary analysis will be assessed against the following efficacy criteria:

- a statistically significant reduction in ESSDAI at Week 13 in the CFZ533 i.v. group compared to placebo, at the one-sided 10% significance level, and
- an estimated mean reduction in ESSDAI in the CFZ533 i.v. group to be 5 points or greater than placebo.

The decrease of 5 points was chosen because it is in the range of what was observed at week 12 in a small open-label study with rituximab ([Meiners et al 2012](#)). A positive sign of efficacy will be considered if both criteria are met.

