### **Handling of missing values/censoring/discontinuations**

All subjects with a baseline ESSDAI and at least one post-baseline ESSDAI will be included in the primary analysis. The planned models assume that missing values are missing at random. The guidelines for subject discontinuation provided in the protocol should ensure that the missingness mechanism is as close as possible to missing at random. The reasonableness of this assumption will be checked and if necessary further methods may be applied.

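### The randomised ESSDAI comparison is analysed by treatment received, and no visible text names its analysis set or says whether an exclusion code overrides the inclusion rule

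*SAP*

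**What the plan says.** **Assignment to groups.** Protocol 9.1: "For all analysis sets, subjects will be analyzed according to the study treatment received". SAP section 5: "For subjects for which the actual treatment received does not match the randomized treatment the treatment actually received will be used for the analysis". Neither makes an exception for the randomised efficacy comparison.

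**Analysis sets.** Protocol 9.1 defines four sets, among them: "The full analysis set will include all subjects that received any study drug". Protocol 9.4 does not tie that set to the primary analysis by name. SAP section 5 and Table 5-1 cover only the safety, PK and PD sets. For the last of these: "The PD analysis set will include all subjects with available PD data and no protocol deviations with relevant impact on PD data". The primary ESSDAI analysis (SAP 7.1.1) stands under the heading "Statistical methods for Pharmacodynamic (PD) parameters", but the text there names no set.

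**Who is in the primary analysis.** SAP 7.1, on missing values, has the same sentence as Protocol 9.4.3: "All subjects with a baseline ESSDAI and at least one post-baseline ESSDAI will be included in the primary analysis".

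**Who can be removed.** Table 5-1 lists code 8, "Exclude from all analyses", and code 22, "Exclude subject from PD analysis set". Codes 5 and 23 also carry a minus in the PD column. The table does not say which deviations receive which code.

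**The concern.** Randomisation makes the two groups comparable. Regrouping patients by what they received, or removing them for a deviation that arose after randomisation, can make group membership depend on prognosis or response. The plan applies the first to the primary comparison by rule. It does not clearly shut out the second.

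The groups are small enough for one patient to count. SAP 7.1.1 gives up the protocol's pooling of placebo patients, so the i.v. comparison rests on Cohort 2 alone: about 30 randomised at 2:1 (20 and 10), with 24 expected to complete (16 and 8). Cohort 1, with about 12 randomised, has about 4 on placebo. Success in the i.v. group requires an estimated benefit of at least 5 points as well as one-sided significance at 10%.

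Blinding protects the coding only in part. Protocol 8.3 has deviations determined before the database is locked and unblinded. However, Protocol Table 18-1 allows the statistician and programmer individual-level unblinding at an interim analysis, and SAP section 3 says that interim analyses had already taken place.

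**Working it through.** **1. The inclusion and exclusion rules side by side**

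| Rule | Reaches the primary ESSDAI analysis? |
|---|---|
| Baseline plus at least one post-baseline ESSDAI (Protocol 9.4.3, SAP 7.1) | Yes, by name |
| Code 8 | Yes, on its wording |
| Codes 5, 22 and 23 | Only if the PD set is used, which is not stated (for code 5, also if the safety set were used) |

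No visible sentence says which rule prevails for a patient who has the required ESSDAI values and also carries code 8.

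**2. The protocol's own figures**

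Inputs from Protocol 9.6 and 9.4.2: 16 v 8 patients, SD 5, one-sided 10% test, estimate of at least 5 points. A simple two-sample comparison is used here in place of the longitudinal model.

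- SE = 5 × √(1/16 + 1/8) = 2.165.
- Significance needs 1.2816 × 2.165 = 2.77 points (2.86 with the t distribution on 22 df), so the 5-point criterion binds.
- P(both criteria) = 1 − Φ((5 − true difference)/SE).

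| True difference | Computed | Protocol 9.6 |
|---|---|---|
| 0 | 1.0% | around 1% |
| 2 | 8.3% | below 10% for differences under 2 |
| 5 | 50% | about 51% |
| 7 | 82.2% | about 83% |

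The stated figures reproduce. For 20 v 10, SE = 1.936 and the results are 0.5%, 6.1%, 50% and 84.9%.

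**3. Excluding one patient**

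The documents give no count of deviations, so one excluded patient is an assumption. If that patient differs by d points from the rest of an arm of n, the arm mean moves by d/n.

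| Arm | n | d = 3 | d = 7 | d = 10 |
|---|---|---|---|---|
| Placebo | 8 | 0.38 | 0.88 | 1.25 |
| Placebo | 10 | 0.30 | 0.70 | 1.00 |
| CFZ533 | 16 | 0.19 | 0.44 | 0.63 |
| CFZ533 | 20 | 0.15 | 0.35 | 0.50 |

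*Exclusion of one placebo patient unrelated to outcome.* There is no bias. With 16 v 7, SE = 2.266 and success at a true difference of 7 is 81%, against 82%. With 20 v 9, SE = 2.007 and success is 84%, against 85%.

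*Worst-case bound.* Suppose the excluded patient is always the least-improved one on CFZ533. The estimate rises by 1.766 × 5/15 = 0.59 (n = 16) or 1.867 × 5/19 = 0.49 (n = 20), where 1.766 and 1.867 are the expected distances of the extreme value from the mean, in SDs. In simulation (400,000 trials per case, pooled t-test plus the 5-point criterion), success at a true difference of 2 rises from about 8% to 13% with 16 v 8, and from about 6% to 10% with 20 v 10.

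**4. One misdosed patient**

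Suppose one placebo-randomised patient receives CFZ533, responds as an active patient does, and was misdosed for reasons unrelated to prognosis. The true difference is 7.

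| Placebo arm | As randomised | As treated |
|---|---|---|
| 8 | 7 × 7/8 = 6.1 points; SE 2.165; 70% | 7.0 points; 17 v 7, SE 2.245; 81% |
| 10 | 7 × 9/10 = 6.3 points; SE 1.936; 75% | 7.0 points; 21 v 9, SE 1.992; 84% |

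**The case against.** **As-treated is a declared choice.** It is the same in both documents, the study is non-confirmatory, and the criteria serve internal decisions. In the misdosing illustration, as-treated recovers the true difference while as-randomised is diluted. That stands as a cost of the change. But the advantage depends on misdosing being unrelated to prognosis, which the analysis cannot guarantee. No misdosing is documented, and Protocol 5.3 asks for a countersigned record of the assignment.

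**The conflict is narrow.** The rule on ESSDAI values is specific and appears twice. It can be read as a minimum-data requirement within some analysis set, in which case it does not collide with the codes. A reader might infer a certain contradiction, or that the PD heading puts the primary analysis on the PD set. The documents support neither. What they show is an ambiguity, limited to code 8 unless the PD set is meant.

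**Escalated treatment is not shown to be a coded exclusion.** A reader might point to Protocol 5.5.8, on patients who need more corticosteroid or an immunosuppressive, as an outcome-related exclusion. That section concerns possible withdrawal, case by case, and mentions no code. Protocol 5.5.10 keeps patients who stop treatment in the study unless they withdraw consent.

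**Interim unblinding may not have touched coding.** Table 18-1 keeps the data manager, study monitor and primary investigator blinded at interim. No visible text says who assigns codes, and the interim sections are redacted. So the blind cannot be shown to cover later coding decisions, nor can a breach be shown.

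**The set may be named elsewhere.** Redacted sections and SAP Modules 7 and 8 were not seen. This limits the claim to visible text. Module 3 is the methodology document, though, and its analysis-sets section is visible.

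**Conclusion.** The point holds in limited form. Both documents analyse the randomised primary comparison by treatment received. No visible text names its analysis set, and code 8 is not reconciled with the rule on who is included. This should be corrected, but its weight is modest and no bias has been demonstrated.

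The effect is nil if nobody was misdosed or coded out. With one excluded patient, it ranges from about one percentage point of power (exclusion unrelated to outcome) to a shift of 0.15 to 1.25 points (one patient 3 to 10 points away from the rest of the arm). All these figures assume SD 5 and a two-sample comparison.

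A reader might take the rise from about 8% to 13% at a true difference of 2 as the expected inflation. It is a worst-case bound: it needs the excluded patient always to be the least-improved one on CFZ533, which no document suggests. With 20 v 10 the same bound reaches only about 10%.

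**What to change.** In SAP section 5, define a full analysis set for ESSDAI and the other comparative efficacy analyses of Cohorts 1 and 2: all randomised and dosed patients with a baseline and at least one post-baseline value, analysed in the group to which they were randomised, with no exclusion by deviation code. This would be a new definition, because the protocol's full analysis set is itself analysed by treatment received and has no post-baseline requirement.

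- Name the set in SAP 7.1 and add it as a column in Table 5-1, so that the codes and the inclusion rule agree.
- Keep treatment received for safety and PK.
- Run the PD set, and an as-treated analysis if anyone was misdosed, only as sensitivity analyses.
- Record the departure from Protocol 9.1 in the SAP, as SAP 7.1.1 already does for placebo pooling, or align 9.1 at the next amendment. An amendment needs the approvals listed in Protocol 11.1, so it is more than an edit.

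The change needs no new data; it costs SAP wording and one table column. The price in information is the dilution shown above (6.1 points and 70% success, against 7.0 and 81%, with one of 8 placebo patients misdosed), which the as-treated run would make visible.

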There is a minimal risk for thromboembolic complications when targeting this co-stimulatory pathway with this anti-CD40 mAb.

Corporate Confidential Information

Although the risk is hypothetical, hematologic and coagulation parameters will be regularly monitored in the current study. Furthermore, patients with conditions such as anti-phospholipid syndrome where the risk is already high will be excluded.

Systemic inflammation and potential kidney injury

Corporate Confidential Information

Although not expected in this clinical study, the investigator will monitor for signs, symptoms and laboratory results consistent with clinically significant inflammation as well as for changes in renal function and signs of acute kidney injury as per local practice.

Lymphadenopathy

Corporate Confidential Information

The investigator will pay special attention to lymph nodes in patients during physical assessments including unusual lymphadenopathy in the absence of infection.
Corporate Confidential Information

Lymphoproliferative disorders

Corporate Confidential Information

The clinician should monitor hematology regularly for changes consistent with a lymphoproliferative disorder.

4 Population

The study population will be comprised of male and female subjects with active primary Sjögren's syndrome.

A total of approximately 12 subjects for Cohort 1, 30 subjects for Cohort 2, and 24 subjects for Cohort 3 are planned to be randomized to participate in the study. Approximately 10 subjects are expected to complete the placebo-controlled period in Cohort 1, approximately 24 subjects are expected to complete the placebo-controlled period in Cohort 2, and approximately 20 subjects are expected to complete the treatment period in Cohort 3.

The investigator must ensure that all subjects being considered for the study meet the following eligibility criteria. No additional criteria should be applied by the investigator, in order that the study population will be representative of all eligible subjects.

Subject selection is to be established by checking through all inclusion/exclusion criteria at screening and baseline. A relevant record (e.g., checklist) of the eligibility criteria must be stored with the source documentation at the study site.

Deviation from **any** entry criterion excludes a subject from enrollment into the study.

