## **2 Study objectives and design**

### **2.1 Study objectives**

#### **2.1.1 Primary objectives**

- To assess the safety and tolerability of multiple subcutaneous doses and multiple intravenous infusion of CFZ533 in patients with primary Sjögren's syndrome (pSS) as measured by adverse events (AEs).
- To compare the effect of multiple intravenous infusion of CFZ533 versus placebo on the clinical disease activity of pSS patients as measured by the change of an EULAR Sjögren's Syndrome Disease Activity Index (ESSDAI) after 12 weeks treatment.

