## **9 Statistical methods for safety and tolerability data**

All data for background and demographic variables will be listed by cohort, treatment group and subject. Summary statistics will be provided by treatment group within cohort.

Relevant medical history, current medical conditions, results of laboratory screens, drug tests and any other relevant information will be listed by cohort, treatment group and subject.

Data for study drug administration (rescue medication) and concomitant therapies will be listed by cohort, treatment group and subject.

Plots to visualize trends in longitudinal safety data (vitals, ECG, lab parameter) will be created.

All vital signs will be listed by cohort, treatment, subject and visit/time and if ranges are available abnormalities (and relevant orthostatic changes) will be flagged. Summary statistics will be provided by cohort, treatment and visit/time.

All ECG data will be listed by cohort, treatment, subject and visit/time, abnormalities will be flagged. Summary statistics will be provided by cohort, treatment and visit/time.

All laboratory data will be listed by cohort, treatment, subject and visit/time and if normal ranges are available abnormalities will be flagged. Summary statistics will be provided by cohort, treatment and visit/time. Individual B-cell and neutrophil counts over time by cohort, treatment group will be presented graphically.

All information obtained on adverse events will be displayed by cohort, treatment and subject. The number and percentage of subjects with adverse events will be tabulated by body system and preferred term with a breakdown by treatment within cohort. A subject with multiple adverse events within a body system is only counted once towards the total of this body system.

The frequency of patients who have had infections by Week 13 will be tabulated and compared between treatment groups within Cohorts 1 and 2 with Fisher's Exact test.

Immunogenicity results will be listed by cohort, treatment, subject and visit/sampling time point. No descriptive summary statistics will be provided.

Corporate Confidential Information

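### The SAP allows dosed subjects to be dropped from the safety analysis set, contradicting the protocol, which keeps everyone who received any study drug

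*SAP*

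**What the plan says.** Protocol Section 9.1 sets no condition beyond dosing: "The safety analysis set will include all subjects that received any study drug". It applies a deviation condition only to the PK and PD sets.

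SAP Section 5 applies one to the safety set as well: "All subjects that received study drug and with no protocol deviations with relevant impact on safety will be included in the safety analysis set".

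SAP Table 5-1 turns this into codes. Code 5 reads "Exclude subject from all safety analysis" and code 8 reads "Exclude from all analyses". Both carry a minus sign in the safety column, and the legend gives the meaning: "include in analysis set, - = exclude from analysis set". Codes 20, 22, 23 and 49 all keep the subject in the safety set.

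The first primary objective in SAP Section 2.1.1 is a safety objective: "To assess the safety and tolerability of multiple subcutaneous doses and multiple intravenous infusion of CFZ533", measured by adverse events. SAP Section 9 describes the main output: "The number and percentage of subjects with adverse events will be tabulated by body system and preferred term", broken down by treatment within cohort. It also compares infections by Week 13 between groups in Cohorts 1 and 2 with Fisher's exact test. Section 9 does not name the analysis set for either output.

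**The concern.** A safety set exists so that harm is counted in everyone exposed. Under the SAP, a dosed subject given code 5 or 8 leaves that set. If the adverse event and infection tables use it, the subject drops out of both numerator and denominator.

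The criterion is applied after randomisation and may be related to the outcome, because a deviation judged relevant to safety may be one where an adverse event is more likely or more informative. The bias could go either way, depending on who is removed and from which arm.

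The available text does not say which deviations receive code 5 or 8, so the rule leaves room for case-by-case judgement. It is also undeclared. SAP Section 7.1.1 says openly that its primary efficacy analysis differs from the protocol, and why. Section 5 says nothing of the kind about the safety set.

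**Working it through.** **The texts side by side**

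| Subject | Protocol 9.1 | SAP Section 5 and Table 5-1 |
|---|---|---|
| Dosed, no deviation | In safety set | In |
| Dosed, code 20, 22, 23 or 49 | In | In |
| Dosed, code 5 or 8 | In | **Out** |

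The third row is the contradiction. Reading codes 5 and 8 as meant only for undosed subjects does not remove it, because the added condition in Section 5 concerns subjects who did receive study drug.

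**How much one exclusion can matter**

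Neither document gives a count of subjects coded 5 or 8. All event and exclusion counts below are therefore assumptions, except the protocol's own Table 9-2 row.

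*Arm sizes.* Protocol Section 4 plans "A total of approximately 12 subjects for Cohort 1, 30 subjects for Cohort 2", and Protocol Section 5.2 randomises these cohorts 2:1. If all are dosed, Cohort 2 has 20 active and 10 placebo, and Cohort 1 has 8 and 4.

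*Largest shift in an arm's rate from removing one subject* is 1/n:
- Cohort 2: 1/20 = 5 points (active), 1/10 = 10 points (placebo).
- Cohort 1: 1/8 = 12.5 points (active), 1/4 = 25 points (placebo).

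*Rate difference, active minus placebo:*

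| Scenario | Calculation | Difference |
|---|---|---|
| Cohort 2, nobody removed | 10/20 − 3/10 | 0.200 |
| Two active removed, both with events | 8/18 − 3/10 | 0.144 |
| Two active removed, neither with events | 10/18 − 3/10 | 0.256 |
| One placebo removed, with event | 10/20 − 2/9 | 0.278 |
| One placebo removed, without event | 10/20 − 3/9 | 0.167 |
| Cohort 1, nobody removed | 4/8 − 1/4 | 0.250 |
| One active removed, with event | 3/7 − 1/4 | 0.179 |
| One active removed, without event | 4/7 − 1/4 | 0.321 |
| One placebo removed, with event | 4/8 − 0/3 | 0.500 |
| One placebo removed, without event | 4/8 − 1/3 | 0.167 |

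*Protocol Table 9-2.* Its row of 8/16 versus 2/8 reproduces with an unpooled Wald 90% interval, d ± 1.645 × √[p₁(1−p₁)/n₁ + p₂(1−p₂)/n₂]: 0.25 ± 1.645 × 0.1976, or −0.075 to 0.575, as printed. Applying exclusions to that row:
- One active subject with an event removed (7/15 vs 2/8): 0.217 (−0.112 to 0.546).
- Two such subjects removed (6/14 vs 2/8): 0.179 (−0.154 to 0.511).
- One placebo subject with an event removed (8/16 vs 1/7): 0.357 (0.058 to 0.656), which no longer includes zero.

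*Infection comparison, Cohort 2, two-sided Fisher's exact test:*

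| Infections, active vs placebo | p |
|---|---|
| 8/20 vs 0/10 (nobody removed) | 0.029 |
| 7/19 vs 0/10 (one infected active removed) | 0.063 |
| 6/18 vs 0/10 (two infected active removed) | 0.062 |
| 8/18 vs 0/10 (two uninfected active removed) | 0.025 |

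**The case against.** The conflict in wording is not in dispute. The case for treating it as minor has five parts.

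- **Timing.** Protocol Section 8.3 has deviations determined before database lock and unblinding, which limits outcome-driven coding. This is partial protection. That section does not mention severity codes, SAP Section 3 says interim analyses have already taken place, Protocol Appendix 6 allows several sponsor roles to be unblinded at an interim, and Cohort 3 is open-label.
- **Meaning.** Set beside the parallel PK and PD wording, the condition may refer to deviations that make safety data unusable, not deviations linked to harm. That is possible, but the available text does not say so, and either reading removes dosed subjects whom the protocol includes.
- **Unseen modules.** Table shells and programming specifications sit in RAP Modules 7 and 8, which may name the analysis set for each table or define the codes. This stands as a limit on what can be said about Section 9. It does not cure Section 5, because SAP Section 1.1 assigns statistical methodology to this module.
- **Consequences.** The study is non-confirmatory, by-subject adverse event displays carry no stated set restriction, and significant deviations are reported in the study report. Events need not disappear from view, but the summary percentages and the infection test could still change.
- **Illustrations.** The counts are invented, neither document gives a significance level for the infection test, and the largest shifts are in Cohort 1, whose subcutaneous safety objective is secondary in the protocol. All of this is fair. The figures show only how sensitive small arms are. Intravenous safety is primary in both documents, so the point does not depend on Cohort 1.

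**Conclusion.** The concern holds. SAP Section 5 and codes 5 and 8 of Table 5-1 permit a dosed subject to be left out of the safety set, whereas Protocol Section 9.1 includes every such subject. The departure is neither declared nor explained, and it affects the population for a primary objective, so it should be corrected and not left to interpretation.

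The effect on results is unknown: the documents do not show that anyone was excluded, and bias could go in either direction. The ceiling per excluded subject is 5 points (active) or 10 points (placebo) in Cohort 2, and 12.5 or 25 points in Cohort 1. This assumes that all planned patients are randomised 2:1 and dosed, and that the tables in SAP Section 9 use the safety set.

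**What to change.** - In SAP Section 5, define the safety set as all subjects who received any study drug, with no deviation condition, as in Protocol Section 9.1.
- Delete code 5 from Table 5-1 and state that code 8 does not remove a dosed subject from the safety set. Keeping the codes for never-dosed subjects only would also resolve the contradiction, provided the table says so.
- Record the deviations concerned under existing code 49 or in listings.
- Present any analysis without these subjects only as a labelled sensitivity analysis.
- State in SAP Section 9 that the adverse event and infection tables use this safety set.

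The cost is a change to Section 5, two rows of Table 5-1 and one sentence in Section 9. If it is classed as a major change under SAP Section 1.2, it needs a new version of RAP Module 3 approved by the trial team. No new data and no protocol amendment are needed.
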